APPENDIX 8: 12-LEAD ELECTROCARDIOGRAM ABNORMALITY CRITERIA

	Potentially Significant Findings Leading to Screen Failure	Potentially Significant Postrandomization Findings (clarification on action to take)
RHYTHM		
Sinus Tachycardia	> 110 bpm	HR > 110 bpm and HR increase of ≥ 25 bpm from baseline, that is sustained for 90 minutes or longer
Sinus Bradycardia	< 40 bpm	HR < 40 bpm and HR decrease of ≥ 5 bpm from baseline
Sinus Pause/Arrest	> 2.0 seconds	> 2.0 seconds
Atrial Premature Complex	> 1 beat	≥ 3 beats
Ventricular Premature Complex	All	≥ 3 beats
Ectopic Atrial Rhythm	None	None
Junctional Rhythm	Junctional Rhythm with HR < 40 bpm	Junctional Rhythm with HR < 40 bpm
Idioventricular Rhythm	All	All
Atrial Fibrillation	All	All
Atrial Flutter	All	All
Supraventricular Tachycardia	All	All
Ventricular Tachycardia	All	All
AXIS		
Left Axis Deviation	RBBB With LAHB	New Onset LAHB
Right Axis Deviation	RBBB With LPHB	New Onset LPHB

	Potentially Significant Findings Leading to Screen Failure	Potentially Significant Postrandomization Findings (clarification on action to take)
CONDUCTION		
1st Degree AV Block	PR \geq 230 ms	PR \geq 230 ms + Increase of $>$ 15 ms; or PR Increase of $>$ 25%
2nd Degree AV Block	Mobitz Type II	Mobitz Type II
3rd Degree AV Block	All	All
LBBB	All	All
RBBB	RBBB With LAHB/LPHB as Defined Above	New Onset RBBB (Not Including Rate-related)
ICRBBB (QRS $<$ 120 ms)	No Exclusion	Nothing
Short PR/Preexcitation Syndrome	Delta Wave + PR $<$ 120 ms	Delta Wave + PR $<$ 120 ms
Other Intra-Ventricular Conduction Delay	QRS \geq 130 ms	QRS \geq 130 ms + Increase of \geq 10 ms
QTc (B or F)		
Male	QTc \geq 470 ms	QTc \geq 500 ms or Increase of \geq 60 ms From Baseline
Female	QTc \geq 480 ms	QTc \geq 500 ms or Increase of \geq 60 ms From Baseline
HYPERTROPHY		
Atrial Abnormalities	Definite Evidence of P Mitrale or P Pulmonale	Definite Evidence of P Mitrale or P Pulmonale
Ventricular Abnormalities	Voltage Criteria for LVH Plus Strain Pattern	Voltage Criteria for LVH Plus Strain Pattern
MYOCARDIAL INFARCTION		
Acute or Recent	All	All
Old	All	All

	Potentially Significant Findings Leading to Screen Failure	Potentially Significant Postrandomization Findings (clarification on action to take)
ST/T MORPHOLOGY		
ST Elevation Suggestive of Myocardial Injury	In 2 or more contiguous leads	In 2 or more contiguous leads
ST Depression Suggestive of Myocardial Ischaemia	In 2 or more contiguous leads	In 2 or more contiguous leads
T-wave Inversions Suggestive of Myocardial Ischaemia	In 2 or more contiguous leads	In 2 or more contiguous leads
Non-specific ST-T Changes (In 2 or More Leads)	No exclusion	In 2 or more contiguous leads
PACEMAKER	All	All
AV=atrioventricular; bpm=beats per minute; HR=heart rate; ICRBBB=incomplete right bundle branch block; LAHB=left anterior hemiblock; LPHB=left posterior hemiblock; LVH=left ventricular hypertrophy; mm=millimeter; ms=milliseconds, PR=pulse rate; QTcB=QT correction using Bazett's formula; QTcF=QT correction using Fridericia formula; RBBB=right bundle branch block; ST/T=ST-segment/T wave. Baseline is defined as Predose Day 1		

APPENDIX 11: DOCUMENT HISTORY

[figure not shown]
Version	Date
Original	12-Mar-2021
Amendment 1	11-May-2021
Amendment 4	17-Dec-2021
Amendment 8	13-May-2022

[figure not shown]
CCI

CCI

CCI

CCI

CCI

CCI

CCI

CCI

CCI

[figure not shown]
CC

CCI

CCI

CCI

CCI

CCI

CCI

CCI

CCI

CCI

CCI

CCI

CCI

CCI

CCI

[figure not shown]

CCI

CCI

[figure not shown]
CCI

CCI

CCI

CCI

CCI

CCI

## DEFINITIONS AND ABBREVIATIONS

ADA	anti-drug antibody
AE	adverse event
ATC	anatomical therapeutic chemical
AUC	area under the curve
AUC 0-inf	area under the curve from time 0 to infinity
AUC 0-t	area under the curve from time 0 to time t
BLRM	Bayesian Logistic Regression Model
C max	maximum concentration
CBT	continued blinded treatment
CRO	contract research organization
DLT	dose-limiting toxicity
DRC	data review committee
ECG	electrocardiogram
eCRF	electronic case report form
FAS	full analysis set
HCP	health care professional
IBDQ	Inflammatory Bowel Disease Questionnaire
IBT	initial blinded treatment
IL-5	interleukin 5
ITT	intent-to-treat analysis set
LOCF	last observation carried forward
LOQ	limit of quantitation
MCS	Mayo score
MedDRA	Medical Dictionary for Regulatory Activities
MES	Mayo endoscopic subscore
mMCS	modified Mayo score
MMRM	mixed-model-repeated measure
MTD	maximum tolerated dose
NCI CTCAE	National Cancer Institute Common Terminology Criteria for Adverse Events
NRI	non-responder imputation
OL	open-label
PD	pharmacodynamics
PGA	physician global assessment
PK	pharmacokinetics
pMCS	partial Mayo score
PP	per protocol analysis set
PT	preferred term
CCI	
RB	rectal bleeding
RHI	Robarts Histopathology Index
RO	receptor occupancy
SAE	serious adverse event
SAF	safety analysis set
SAP	statistical analysis plan
SC	subcutaneous
sCD25	soluble form of IL2 receptor alpha chain
SF	stool frequency
SOC	system organ class

TEAE	treatment-emergent adverse event
TESAE	treatment-emergent serious adverse event
TMF	trial master file
Treg	regulatory T cell
UC	ulcerative colitis
ULN	upper limit of normal
WHODD	World Health Organization drug dictionary

## 1 INTRODUCTION

This is a Phase 1b, adaptive, randomized, double-blind, placebo-controlled, multiple-dose study. This study will evaluate the safety, tolerability, pharmacokinetics (PK), and pharmacodynamics (PD) of PT101 in subjects with active ulcerative colitis (UC) following multiple subcutaneous (SC) doses.

### 1.1 OBJECTIVE OF THE STATISTICAL ANALYSIS PLAN

This statistical analysis plan (SAP) describes in detail the statistical methods that will be applied to the data gathered in clinical trial protocol No. PT101-201. It will describe the statistical analysis methods and data presentations to be used in tables, figures, and listings (TFLs), to assess the safety, PK, PD, and efficacy in patients with mildly to severely active UC. It will also outline the data analyses performed for the data review committee (DRC). This SAP will be finalized prior to database lock and the data analysis start. Any changes to the planned analyses (other than cosmetic) made after database lock will be documented in the clinical study report with rationales and details.

Safety, PK, PD, and efficacy analyses defined within this SAP will be periodically presented to the DRC to inform their recommendation on dose-escalation, opening of an optional cohort, continuing the study without changes, modifying the study, and/or dose/regimen selection to guide future clinical development of PT101 as outlined in the DRC charter. Roles and responsibilities of the DRC are also described in the DRC charter.

## 2 STUDY OBJECTIVES

This document will present analysis related to the primary (safety), secondary (PK, PD, immunogenicity), and exploratory clinical efficacy (assessment of improvement in disease activity) endpoints through **CC1** and applicable efficacy and safety endpoints **CC1**. All primary, secondary, and exploratory endpoints are described in more detail in [Table 1](#). All analyses specific to exploratory biomarkers will be described in a separate translational analysis plan.

### 2.1 OBJECTIVES AND ENDPOINTS

**Table 1. Objectives and Endpoints**

Objectives	Outcomes
Primary Objectives	Primary Endpoint
To evaluate the safety and tolerability of PT101 in subjects with active UC following multiple SC doses	

Safety and tolerability as assessed by incidence of TEAEs, TESAEs, and changes in laboratory values, ECGs, physical exam findings, and vital signs through CC1

Secondary Objectives	Secondary Endpoint
To assess the PK of PT101 in subjects with UC following multiple SC doses	

PK parameters of PT101 through CC1 (as described in Table 7)

Change in serum concentration of PT101 over time

To assess the PD of PT101 in subjects with UC following multiple SC doses	

PD parameters of PT101 through CC1 (as described in Table 8/Table 9)

To assess the immunogenicity of PT101 in subjects with UC following multiple SC doses	

Anti-drug antibodies to PT101 through CC1

To assess the PK/PD relationship of PT101 in subjects with UC following multiple SC doses	
 
The relationship between the PT101 PK and PD response
 

Exploratory Objectives	Exploratory Endpoint
To assess improvement in disease activity in subjects with UC following multiple SC doses of PT101	
 
Mean change from baseline in modified Mayo Score at [REDACTED] CCI [REDACTED]
 
Mean change from baseline in total Mayo Score at [REDACTED] CCI [REDACTED]
 
Mean change from baseline in partial Mayo Score at [REDACTED] CCI [REDACTED]
 
Mean change from baseline in Robarts Histologic Index score at [REDACTED] CCI [REDACTED]
 
Mean change from baseline in UC-100 score at [REDACTED] CCI [REDACTED]
 
Mean change from baseline in patient-reported outcome measures at [REDACTED] CCI [REDACTED] 
 
IBDQ
 
SF-36
 
 
 
Proportion of subjects achieving clinical remission at [REDACTED] CCI [REDACTED]
 
Proportion of subjects achieving endoscopic improvement at [REDACTED] CCI [REDACTED]
 
Proportion of subjects achieving clinical response at [REDACTED] CCI [REDACTED]
 
Proportion of subjects achieving symptomatic remission at [REDACTED] CCI [REDACTED]
 
Proportion of subjects achieving symptomatic response at [REDACTED] CCI [REDACTED]
 
Proportion of subjects achieving endoscopic remission at [REDACTED] CCI [REDACTED]
 
Proportion of subjects achieving histologic remission at [REDACTED] CCI [REDACTED]
 
Proportion of subjects achieving histologic response at [REDACTED] CCI [REDACTED]
 
Proportion of subjects achieving mucosal healing at [REDACTED] CCI [REDACTED]
 
Change from baseline in partial Mayo Score beyond [REDACTED] CCI [REDACTED]
 
Incidence and characterization of TEAEs and laboratory abnormalities beyond [REDACTED] CCI [REDACTED]
 

To evaluate changes in PT101- and UC-associated biomarkers following multiple SC doses of PT101	
 
Mean change from baseline in FC at [REDACTED] CCI [REDACTED]
 
Mean change from baseline in hs-CRP levels at [REDACTED] CCI [REDACTED]
 
Changes in PT101 and UC-associated biomarkers 
 
sCD25
 
IL-5
 
IFN-γ, IL1-B, IL-2, IL-4, IL-6, IL-8, IL-10, IL12p70, IL-13, TNF-α
 
TSDR FOXP3 Assay (Treg cells)
 
TSDR CD4 Assay (CD4 T cells)
 
 
 

ECG = electrocardiograms; FC = fecal calprotectin; hs-CRP = high sensitivity C-reactive protein; IBDQ = Inflammatory Bowel Disease Questionnaire; IL-5 = interleukin 5; PD = pharmacodynamics; PK = pharmacokinetics; SC = subcutaneous; sCD25 = soluble form of IL2 receptor alpha chain; SF = Short Form-36; TEAE = treatment-emergent adverse event; TESAE = treatment-emergent serious adverse event; TSDR = Treg-specific demethylated region; UC = ulcerative colitis

### 3 STUDY DESIGN

#### 3.1 SUMMARY OF STUDY DESIGN

The study will enroll up to approximately 60 subjects with mildly to severely active UC in up to 6 cohorts of 10 subjects each (randomized 4:1 [PT101:placebo]) in a multiple ascending doses design. There will be 3 planned cohorts (Cohorts 1 to 3) and up to 3 optional cohorts (Cohorts 4 to 6). Subjects in Cohort 1 will receive PT101 or placebo [REDACTED] CCI [REDACTED] for a total of [REDACTED] CCI [REDACTED] Cohorts 2 and 3 will receive PT101 or placebo [REDACTED] CCI [REDACTED] for a total of [REDACTED] CCI [REDACTED]

period. Subject randomization will be stratified by prior advanced therapy use (yes or no). Enrollment of subjects with a prior history of inadequate response, loss of response, or intolerance to 2 advanced therapies as assessed by the Investigator will be capped at 20% of subjects per cohort.

Subjects who have achieved clinical response (based on the modified Mayo Score [mMCS] using the endoscopic subscore [MES] derived by the Investigator) at CCI will be eligible to enter the continued blinded treatment (CBT) phase of the study. Subjects in the CBT phase will receive the same treatment allocation (PT101 or placebo) as received during the initial blinded treatment (IBT) phase; subjects who received PT101 will continue receiving PT101 at the same dose/regimen. Corticosteroid tapering will be initiated at CCI of the IBT phase for subjects entering the CBT phase. Subjects who enter the CBT phase will receive their first dose of blinded study drug on CCI for both dosing regimens CCI

CCI Subjects who do not achieve clinical response at CCI will have the option to enter an open-label (OL) phase of the study. Subjects in the OL phase will receive PT101 at the same dose/regimen as received by subjects in their cohort during the IBT phase. Subjects participating in the OL phase who achieve a clinical response using the partial Mayo Score (pMCS) at CCI of the OL phase will also undergo corticosteroid tapering. Subjects who do not achieve a clinical response using the pMCS at CCI of the OL phase may continue on open-label treatment if it is considered in the best interest of the subject at the discretion of the investigator. Subjects who enter the OL phase will receive their first dose of PT101 on CCI for both dosing regimens CCI

Subjects with insufficient data to assess clinical response at CCI of IBT will not be eligible to enter the CBT or OL phases and will be discontinued from the study.

A DRC composed of unblinded members not involved in any way in the conduct of this trial will assess safety, PK, and PD data and provide recommendations on dose escalation/dosing regimen CCI study continuation, and enrollment of subjects into the 3 planned cohorts (Cohorts 1-3) and the 3 optional cohorts (Cohorts 4-6), as well as provide recommendations on dose and dosing regimen selection to inform future clinical development.

The schedules of assessments are presented in [Appendix A](#).

### 3.2 TREATMENTS

Subjects in Cohorts 1 to 3 will receive placebo or PT101 at a dose of CCI CCI If optional cohorts are added based on a DRC review, no subject will receive a dose CCI

### 3.3 RANDOMIZATION AND BLINDING

#### 3.3.1 RANDOMIZATION

The randomization schedule will be generated using an interactive web response system (IWRS). The investigator should assign the responsibility of unblinded health care professional (HCP) to a qualified person who will prepare the study drug and will not participate in the evaluation of any study subject. All randomization information will be stored in a secured area, accessible only by the unblinded HCP.

### 3.3.2 BLINDING

The unblinded HCP will prepare and transfer study drug (PT101 and placebo) to the investigator or qualified designee for study drug administration. Contact between the unblinded HCP and study subjects should be avoided in order to protect the blind. Blinding is accomplished by the random, masked, assignment of allocation numbers to the treatment groups, and by ensuring the drug supplies administered in the treatment groups appear identical.

Information necessary to unblind a treatment assignment at the investigator's site is held by the unblinded HCP in the form of treatment codes. Should a situation arise which requires unblinding of the treatment assignment, the treatment code(s) will be provided according to the process defined in the clinical trial integrity plan. Upon unblinding, the subject should undergo the end of study (EOS) visit if possible and be followed for safety purposes. In the event of an accidental unblinding of treatment assignment, the medical monitor should be promptly notified. At the end of the study, all records for premature unblinding must be returned to the sponsor and filed in the trial master file (TMF).

Selected individuals from the sponsor, contract research organization (CRO), an independent statistician, and the DRC will be unblinded to treatment assignments. The purpose of having unblinded personnel is to monitor study conduct, prepare data for presentation to the DRC, and to facilitate planning for subsequent dosing cohorts. All unblinded personnel will be fire-walled from the operational study team at the sponsor and CRO to prevent inadvertent unblinding of treatment assignment and to minimize the risk of introducing bias into the study results. Designation of unblinded study personnel will be authorized by the sponsor's clinical director and the lead study biostatistician. A roster of unblinded personnel will be maintained in the TMF and in the clinical trial integrity plan. All unblinded personnel will be trained in steps necessary to maintain an adequate firewall.

## 4 GENERAL CONSIDERATIONS FOR DATA ANALYSIS

### 4.1 REPORTING CONVENTIONS

The summary tables, figures, and by-subject listings will be prepared using the following conventions:

- Unless otherwise specified, the baseline value is defined as the last non-missing assessment prior to the first dose of study treatment. The last non-missing evaluation includes unscheduled and repeat visits.
- If the date of interest occurs on or after the first dose/randomization date, the study day will be calculated as “date of interest – date of first dose/randomization + 1”.
- If the date of interest occurred prior to the first dose/randomization date, then study day will be calculated as “date of interest – date of first dose/randomization”.
- Both safety and efficacy analysis results will be presented using descriptive statistics. Depending on the parameter, the difference from baseline will either be computed using the original scale (raw change from baseline) or on the log scale and back transformed for reporting.
- Categorical data will be summarized by treatment group in terms of frequency counts and percentages.
- Continuous variables will be summarized by treatment group using descriptive statistics (the number of subjects [n], mean, median, SD, minimum, and maximum) of the values at each visit and the change from baseline to each visit. PK parameters and other laboratory analytes that are believed to follow an

approximate log-normal distribution will also be summarized by the geometric mean and coefficient of variation (expressed as a percent).

- CIs will be presented as 2-sided 95% CIs.
- All mean, median, and CI values will be formatted to one more decimal place than the measured values. SD values will be formatted to two more decimal places than the measured value. Minimum and maximum will be formatted to the same number of decimal places as the measured value. The maximum number of decimal places reported shall be four for any summary statistic.
- All percentages will be rounded to one decimal place. The number and percentage of responses will be presented in the form XX (XX.X), where the percentage is in the parentheses.
- Change from baseline is calculated as a post-baseline value minus the baseline value.
- All laboratory data will be reported using standard international units.
- All analyses and summary tables will include the analysis set sample size (i.e., number of subjects) in the column headings.
- Listing will include both the randomized treatment and actual treatment, if different.
- By-subject listings will be presented for all subjects in the relevant analysis sets, and sorted by treatment allocation, study site (if applicable), subject ID, date, and visit. Numeric data will be listed to the same number of decimal places as recorded on the electronic case report form (eCRF) or other data source. Data collected on log forms, such as adverse events (AEs), will be presented in chronological order within the subject.
- SAS® Software Version 9.4M5 (SAS Institute Inc., Cary, NC, USA.) is to be used for all analyses including tables, listings, and figures.
- Partial dates will be imputed as follows:
  - If day and month is missing but year is present, the 1st of July of the noted year will be used.
  - If day is missing but year and month are present, the 15th of the noted month and year will be used.
- Non-PK lab data that are continuous in nature but are less than the lower limit of quantitation (LOQ) or above the upper LOQ will be imputed as follows:
  - A value that is 1/10th unit less than the lower LOQ will be used for calculation of descriptive statistics if the datum is reported in the form of “ $< x$ ” (where x is considered the lower LOQ). For example, if the values are reported as  $< 50$  and  $< 5.0$ , values of 49 and 4.9, respectively, will be used for calculation of summary statistics. An exception to this rule is any value reported as  $< 1$  or  $< 0.1$ , etc. For these, a value of 0.9 or 0.09, respectively, will be used for calculation of summary statistics.
  - A value that is 1/10th unit above the upper LOQ will be used for calculation of descriptive statistics if the datum is reported in the form of “ $> x$ ” (where x is considered the upper LOQ). Values with decimal points will follow the same logic as above. The LOQ will be used for calculation of descriptive statistics if the datum is reported in the form of “ $\leq x$ ” or “ $\geq x$ ” (where x is considered the LOQ).
- PT101 plasma concentration values that are equal to or below the LOQ will be interpolated to 50% of the lower LOQ for the analytical assay throughout the dataset.

- Medical Dictionary for Regulatory Activities (MedDRA) version 24.0 or newest will be used to code AEs and medical history, World Health Organization drug dictionary (WHODD) version Sep 2021 or newest will be used for medication coding.

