3.1.3 Study Periods

The study will be conducted as follows:

- **Screening Period:** will begin when the informed consent form (ICF) is signed. During this period, a subject will undergo baseline assessments to determine eligibility for study participation. Endoscopy (flexible sigmoidoscopy or colonoscopy as indicated)

will be performed, a stool sample will be collected, and additional disease assessment tools will be completed. The screening period will last approximately 4 weeks (\pm 1 week); it will end after all assessments required to assess eligibility have been completed. If a subject meets all eligibility criteria, they will be offered enrollment into the study.

- **Initial Blinded Treatment Phase:** will begin on Day 1 with randomization and the first dose of study drug (PT101 or placebo) administered. The IBT phase will have a duration of 12–14 weeks ^{CCI}
[REDACTED]
- Following completion of the IBT phase, subjects who are eligible may decide to enter into the 9-month CBT or OL phase.

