6.4.2 Open-Label Phase

Subjects who are eligible to enter the OL phase as described in Section 3.1.2 will receive their first dose of PT101 (there is no Placebo treatment arm in the Open-Label Phase) on Day 85. [REDACTED] Assessments in this phase will mainly assess safety and exploratory efficacy. [REDACTED] Subjects will have a safety follow-up visit approximately 28 days after their last dose of study drug. They will also receive a follow-up call approximately 90 days after the final dose of PT101 to assess any changes in UC disease status. Subjects will be asked whether their UC is active, whether they have experienced a UC flare (defined as period of active symptoms), and whether they have started a new therapy for UC.

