#### 4.3 HANDLING OF DATA

In general, missing data will not be imputed unless methods for handling missing data are specified. For purposes of the DRC safety assessment, all results will be presented ‘as observed’ with missing values not imputed. The handling of missing data in analyses of the efficacy endpoints is discussed in Section 6.2.4.

If multiple valid, non-missing, continuous measurements or visits (regardless if it’s scheduled or unscheduled) occurring within a single visit, records will be chosen based on the following rules if a single value is needed:

- For baseline, the baseline value will be the last non-missing value prior to the first dosing of study drug; if multiple measurements occur on the same day, the last non-missing value prior to the time of first dosing of study drug will be considered as the baseline value. If these multiple measurements occur at the same time or the time is not available, the average of these measurements will be considered the baseline value.
- For post-baseline values:
  - a. The record closest to the nominal day for that visit will be selected.
  - b. If there are 2 records that are equidistant from the nominal day, the later record will be selected.
  - c. If there is more than 1 record on the selected day, the average will be taken.

If multiple valid, non-missing, categorical observations exist for one visit, records will be selected as follow:

- For baseline, the last available record prior to the first dose of study drug will be selected. If there are multiple records at the same time or no time recorded on the same day, the worst value will be selected unless otherwise specified.
- For post-baseline values:
  - a. The record closest to the nominal day for that visit will be selected.
  - b. If there are 2 records that are equidistant from the nominal day, the later record will be selected.
  - c. If there is more than 1 record on the selected day, the value with the worst severity will be used.

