### 7.3.1 IMMUNOPHENOTYPING OF CELL POPULATIONS ASSESSMENT

Whole blood will be collected for flow cytometry analysis to evaluate and quantify T, B, natural killer, and Tregs cells. Only data from Immunophenotyping flow cytometry samples that pass Merck sample quality review (Pass/Fail criteria documented in Merck ELN) will be transferred from PPD for analysis. All reportable cell populations and calculations that will be performed are defined [Table 8](#).

Immunophenotyping PD analyses listed in [Table 8](#) will be summarized by dose group at each timepoint, except for maximum fold change from baseline. The maximum absolute change from baseline and maximum fold-change from baseline may be calculated for each cell population. Individual subject level immunophenotypic PD data will be provided in supplemental by-subject listings. Supplemental time course immunophenotyping profile figures will be developed for each cell population type assessed showing mean immunophenotyping parameter level with SD error bars versus time (actual day of collection), doses and dosing regimen. Baseline used in calculations will be defined as the average level of the screening sample and the Day 1 pre-dose sample. If in the event only one sample was available, that sample would be utilized to determine baseline. CD25 mean fluorescence intensity on Tregs will be analyzed at each timepoint.

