#### 9.1.5 TREATMENT-EMERGENT ADVERSE EVENTS

AEs will be defined as treatment-emergent if they are newly occurring or worsen following exposure to study treatment. All AEs reported following exposure to study treatment are considered TEAEs.

TEAE are defined as 1 or both of the following:

- AE onset date  $\geq$  1st study treatment start date/time; or
- AE onset date  $<$  1st study treatment start date/time and either:
  - The severity worsened on or after the 1st study treatment start date/time; or
  - The event became serious on or after the 1st study start treatment date/time

If the onset date of AE is later than the last dosing date of study treatment, then the event is considered AE in follow-up period.

If the onset date of AE is incomplete and the AE stop date is not prior to the first dosing date of study treatment, then the month and year (or year alone if month is not recorded) of onset determine whether an AE is treatment-emergent. The event is considered treatment-emergent if both of the following 2 criteria are met:

- The AE onset/severity worsened is the same as or after the month and year (or year) of the first dosing date of study treatment, and

- The AE onset/severity worsened is the same as or before the month and year (or year) of the last dosing date of study treatment

An AE with completely missing onset and stop dates, or with the onset date missing and a stop date later than the first dosing date of study treatment, will be considered to be treatment-emergent. In addition, an AE with onset date missing and incomplete stop date with the same or later month and year (or year alone if month is not recorded) as the first dosing date of study treatment will be considered treatment-emergent. All AEs that occur after the safety reporting period and are considered study treatment-related in the opinion of the investigator will also be included. All non-treatment-emergent AEs will be included in the listing.

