### 12 CONTINUED BLINDED TREATMENT AND OPEN-LABEL ANALYSIS

Any efficacy, safety, PK, and PD data assessments that are completed during safety follow-up, CBT and OL phase will be analyzed and summary tables will be provided.

Safety data will be analyzed based on the methods described in [Section 9](#) PK and PD data will be analyzed based on the methods described in [Section 7](#). Immunogenicity assessments outlined in [Section 7.2](#) may also be further analyzed during the CBT and OL phase. Efficacy endpoints that are assessed in the CBT and OL phase will be analyzed based on the methods described in [Section 6.2](#). All data for the CBT and OL phase will be summarized up until [CCI](#) or until subject's discontinuation from the study.

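### For placebo subjects who first receive PT101 in the open-label phase, the SAP keeps the pre-placebo baseline and treatment-emergent date

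*SAP*

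**What the plan says.** **Baseline.** SAP 4.1 gives the general rule, which applies wherever no other is specified: "the baseline value is defined as the last non-missing assessment prior to the first dose of study treatment". SAP 4.3 repeats it for repeated measurements: "the baseline value will be the last non-missing value prior to the first dosing of study drug". Immunophenotyping has its own rule in SAP 7.3.1, also placed before any dosing: "Baseline used in calculations will be defined as the average level of the screening sample and the Day 1 pre-dose sample".

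**First dose.** Protocol 3.1.3 says that the initial blinded treatment (IBT) phase "will begin on Day 1 with randomization and the first dose of study drug (PT101 or placebo) administered". Study drug therefore includes placebo.

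**OL phase.** Under Protocol 3.1.2, Week 12 non-responders may opt into OL and receive PT101 at their cohort's dose and regimen. Protocol 6.4.2 states that they "will receive their first dose of PT101 (there is no Placebo treatment arm in the Open-Label Phase) on Day 85".

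**Adverse events.** SAP 9.1.5: "AEs will be defined as treatment-emergent if they are newly occurring or worsen following exposure to study treatment". The detailed criteria count an event with onset on or after the first study treatment. An event with earlier onset counts only if it worsens or becomes serious after that date. SAP 9.1.6 tabulates treatment-emergent events by period.

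**OL analysis.** SAP 12: "Safety data will be analyzed based on the methods described in" SAP Section 9, and PK and PD data follow Section 7. It sets no OL baseline, no OL treatment-emergent date and no grouping for subjects who move from placebo to PT101. SAP 5.6 does restart the clock at OL Visit 1 dosing, but only for duration of exposure.

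**The concern.** Subjects who move from placebo to PT101 are the only people in OL having their first exposure to the drug. Mild eosinophilia was among the most common events in the concurrent healthy-subject trial (Protocol 1.3), and Treg expansion is the intended effect (Protocol 3.2.2). Eosinophil, liver-test, vital-sign and Treg changes after a first dose are therefore what a reader would look for in these subjects.

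Under the stated rules, those changes are measured from a value taken about 12 weeks before PT101 was started. A rise on placebo can appear as a PT101 change, and a fall on placebo can hide one. Treatment-emergent events and laboratory abnormalities beyond Week 12 are a named exploratory endpoint (Protocol 2.2.3). The Data Review Committee (DRC) also sees cumulative safety, PD and biomarker data on all treated patients (SAP 13).

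**Working it through.** The plan gives no figure to reproduce. The check applies its definitions to a subject on placebo from Day 1 and on PT101 from Day 85.

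**1. Gap between baseline and first PT101 dose.** 85 − 1 = 84 days, or 12 weeks. The immunophenotyping baseline is partly older still, because it averages in a screening sample.

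**2. What the OL change contains.** Let B be the SAP baseline, W the Day 85 pre-dose value and X a value in OL.

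- SAP change: X − B = (W − B) + (X − W), the placebo change plus the PT101 change.
- SAP fold change for cell counts: X/B = (W/B) × (X/W).
- A pre-PT101 baseline leaves only X − W, or X/W.

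Hypothetical eosinophil counts in giga/L show that the error can go either way:

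- B = 0.3, W = 0.7, X = 0.7: the SAP change is +0.4 and the change on PT101 is 0.
- B = 0.7, W = 0.3, X = 0.7: the SAP change is 0 and the change on PT101 is +0.4.

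Laboratory shift tables inherit the same problem. A value that goes from normal to high on placebo and stays high is tabulated in OL as a normal-to-high shift.

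**3. Adverse events under the two clocks.**

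| History | SAP clock (Day 1) | Clock from first PT101 dose |
|---|---|---|
| (a) New onset in OL | Emergent by onset | Emergent by onset |
| (b) Onset on placebo, worsens in OL | Emergent by onset on placebo; worsening clause not reached | Emergent by worsening on PT101 |
| (c) Onset on placebo, no worsening | Emergent by onset on placebo | Not emergent |
| (d) Onset in screening, worsens in OL | Emergent by worsening; period not stated | Emergent by worsening on PT101 |

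The by-period tables deal with (a), and they can hold (c) in IBT. For (b) and (d), no rule says which period receives the worsening.

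**4. How many subjects.** Protocol 9.1 gives 8 PT101 and 2 placebo per cohort of 10. The ceilings are 2 per cohort, 2 × 3 = 6 in the planned cohorts, and 2 × 6 = 12 if all six cohorts open. Only non-responders who opt in are affected.

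**5. Share of OL subjects.** The documents give no response rates. Assume that all non-responders enter, with non-response of 60% to 100% on placebo (p) and 30% to 70% on PT101 (a). The share of OL on first exposure is 0.2p / (0.2p + 0.8a).

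- Lowest: 0.12 / (0.12 + 0.56) = 18%.
- Highest: 0.20 / (0.20 + 0.24) = 45%.

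**The case against.** **The AE rule is silent rather than wrong.** A reader might infer that worsening on PT101 is always filed under placebo and never counted as PT101-emergent. The SAP does not say that. It gives no period-assignment rule, and Protocol 7.6.1.1 requires changes in AE severity to be recorded. If sites enter a worsening as a new record, it becomes an OL event. This objection stands, so the supportable claim is that such worsening can be missed.

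**New events are safe.** A reader might add injection site reactions to the harm. A reaction to a first PT101 injection has its onset in OL and is already counted there. This stands too.

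**The data remain visible.** SAP 9.3 and 9.4 report values at each visit as well as changes, with listings, and SAP 7.3.1 adds subject-level cell data. A change from Day 85 could be worked out by hand where a pre-dose value exists. The eosinophil-count thresholds and liver criteria in Protocol 3.1.7 and 7.6.1.6 are absolute values or multiples of the upper limit of normal. This limits the harm, but the planned change and shift tables still carry the wrong comparison.

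**PD in OL cannot be confirmed.** The assessment schedules are redacted, and Protocol 6.4.2 describes OL as mainly safety and exploratory efficacy. The PD part therefore applies only to immunophenotyping that is actually done in OL.

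**Conclusion.** The baseline part holds as written. For placebo subjects entering OL, the stated rules give an OL change equal to the placebo-period change plus the PT101 change. That follows from the definitions and needs no assumption. The adverse-event part holds as a gap: a worsening that crosses from placebo to PT101 has no assigned period.

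The reach is limited. The Week 12 primary safety analysis and the continued blinded phase, where allocation is unchanged, are not affected. What is affected is exploratory OL safety and PD beyond Week 12, and any cumulative DRC display built from the same definitions. Safety is descriptive, so no test is biased.

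Two larger readings are not supported. A reader might take 12 of 60 as the expected number. It is a ceiling that needs all six cohorts to open and every placebo subject to be a non-responder who opts in. A reader might also claim a specific loss of precision from the older baseline. That would depend on correlations between visits, which the documents do not give. The 18% to 45% share rests on assumed response rates and full uptake of OL.

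**What to change.** Add to SAP 12, for subjects who received placebo in IBT and enter OL:

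- The baseline for OL safety and PD analyses is the last available assessment before the first PT101 dose. The existing baseline stays for IBT displays.
- Adverse events that begin or worsen on or after the first PT101 dose count as OL (PT101-emergent) events, including those with onset in IBT or screening.
- OL tables show placebo-to-PT101 and PT101-to-PT101 subjects in separate columns.

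Pre-dose values should exist for much of this. Day 85 is the Week 12 visit (Protocol 6.4), and safety, PK and PD procedures come before dosing on dosing days unless otherwise stated (Protocol 5.1.2). Because the schedules are redacted, the wording should rely on whatever Day 85 pre-dose data were collected.

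The cost is a second baseline flag, a PT101 start date in the analysis datasets, and extra columns with small numbers. The date of any worsening must be recoverable from the AE records. Separate columns reveal IBT allocation, so during the study they belong in the DRC's unblinded closed sessions. No dose or clinical rule changes.
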